6.3 Other outcomes

- **MUST:** the Malnutrition Universal Screening Tool will be used at baseline and end of treatment (T2) to determine the risk of malnutrition.
- **Adverse events:** Possible adverse events including nausea, vomiting and gastrointestinal complaints will be identified by the "symptom diary". Unless we do not expect serious adverse events to occur, patients will be asked to contact a staff member and the researcher directly when adverse events occur. We will only report (serious) adverse events that have a possible causal relationship with the given food products till the end of the study. All AEs will be followed until they have abated, or until a stable situation has been reached.

Table 1. Measurements at each time point

	T0		T1	T2	T3
	Preoperative out-patient clinic	Contact by telephone	Baseline	End of treatment	30 days after surgery
Patient information	X				
Informed consent		X			
Randomization		X			
Handgrip strength			X	X	
Weight			X	X	
PG-SGA			X	X	
Nutritional intake			X	X	
Satisfaction				X	
SF-36			X	X	X
SPPB			X	X	X
Postoperative complication					X
Adverse events			X	X	X

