6.2 Secondary outcomes

- Functional status: besides HGS, change in functional status will be evaluated with the Short Physical Performance Battery.
- Nutritional status: change in nutritional status will be assessed with the PG-SGA and measurements of body weight (table 1).(18) PG-SGA will be filled in by the patient and a member of the research team. Body weight will be measured on a calibrated weighting scale (type ..) in sober state. Relative weight changes will be presented as the percent weight change relative to the weight at baseline. Body Mass Index will be calculated.
- Nutritional intake: difference in nutritional intake (protein and energy) will be evaluated at every time point based on a 2-day food diary filled in by the patient. The food diary will be cross checked by a member of the research team and, if necessary, the patient will be called for clarification. The food items will be coded and calculated according to the Dutch Food Composition Table (NEVO, RIVM). During the pilot study, we will evaluate if a "symptom diary" should be assessed.
- Length of hospital stay and readmission: reported from the medical record of the patients.
- Postoperative complications: reported from the medical record of the patients and classified using the Clavien-Dindo classification.(19) Grade of severity is based on the type of treatment for the specific complication. Infectious complications will be reported based on the definition of the American College of Chest Physicians/Society of Critical Care Medicine Consensus Conference.(20)
- Quality of life: change of quality of life will we assessed with the SF-36 questionnaire filled in by the patients. The Caregiver Reaction Assessment will be filled in by their caregiver.(21)
- Patient satisfaction:
 - o Both groups will fill in a questionnaire with questions about their wellbeing and stress level regarding shopping and cooking of their meals.
 - o In the intervention group, the Net Promoter Score (NPS) with additional questions will be used to assess patient satisfaction in the intervention group at time point 3. The NPS is determined by asking the question: 'How likely is it

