7.2 AEs, SAEs and SUSARs

7.2.1 Adverse events (AEs)

Adverse events are defined as any undesirable experience occurring to a subject during the study, whether or not considered related to the Food for Care products. All adverse events reported spontaneously by the subject or observed by the investigator or his staff will be recorded.

Our proposition will be to only register adverse events that have a possible causal relationship with the given food products. Examples of these events include gastrointestinal complaints and allergic reactions.

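### The symptom diary that section 6.3 relies on for nausea, vomiting and gastrointestinal complaints is optional in 6.2 and absent from Table 1, so these events may have no solicited collection and no defined baseline

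*Combined protocol and SAP*

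**What the plan says.** Three places in the combined protocol and SAP deal with how food-related symptoms are found, and they do not agree.

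- **Section 6.3 (Other outcomes)** treats the diary as settled: "Possible adverse events including nausea, vomiting and gastrointestinal complaints will be identified by the" symptom diary. It adds a second route, under which "patients will be asked to contact a staff member and the researcher directly when adverse events occur".
- **Section 6.2 (Secondary outcomes), under nutritional intake,** treats it as open: "During the pilot study, we will evaluate if a" symptom diary is to be used at all.
- **Table 1** has no diary row. It does have a row for adverse events, marked at T1, T2 and T3 with no restriction by arm, but with no instrument, question list or recall period.

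Section 7.2.1 describes collection as follows: "All adverse events reported spontaneously by the subject or observed by the investigator or his staff will be recorded". It then narrows what is kept: "Our proposition will be to only register adverse events that have a possible causal relationship with the given food products". On the kind of event expected, it says: "Examples of these events include gastrointestinal complaints and allergic reactions". Section 8 describes no analysis of symptoms or adverse events.

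**The concern.** The protocol names the complaints it expects the meals might cause, and names one instrument for asking about them. That instrument depends on a pilot whose result, decision rule and fallback are not given. If the pilot decides against a diary, 6.3 refers to a tool that does not exist, and the remaining text describes only unsolicited reporting.

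Two things are at stake. The first is detection: mild nausea or bowel complaints are easily left unmentioned when nobody asks. The second is attribution. The inclusion criteria admit patients awaiting colorectal and oesophageal surgery, some of whom may plausibly have such symptoms already. Without a defined symptom record at T1, a complaint noted during the three weeks cannot be reliably classed as new, worse or long-standing. The judgement of possible causal relationship that 7.2.1 requires would then have little to rest on.

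**Working it through.** No arithmetic applies: the plan states no figure on this point, and the documents give no symptom or reporting rates. The check sets the sections side by side.

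1. **Is the diary certain?** Section 6.3 says yes; 6.2 says it depends on the pilot. No later section reports the outcome or says what follows if the answer is no.
2. **Is the diary scheduled?** It has no row in Table 1. Its content, timing, recall period and the arms that would complete it appear nowhere.
3. **Does the adverse-event row in Table 1 fill the gap?** In part. It fixes three time points in both arms, and 6.4 has research assistants carrying out the control arm's measurements at home at the set time points. It does not say how events are to be elicited. The text that would supply the method, 6.3 and 7.2.1, offers only the diary, patient-initiated contact, spontaneous report and staff observation. Without the diary, none of these is a question put to the patient.
4. **Is there a baseline?** The row is marked at T1, but with no symptom list or reference period there is no defined T1 record against which a T2 complaint could be called new or worse.
5. **Would the two arms yield comparable records?** Section 7.2.1 first says all reported or observed events are recorded, then proposes to register only those possibly caused by the supplied food. Section 3.2 says the control group receives no additional products. Under that filter no control event can qualify, so there is no control count to set beside the intervention count, however events are detected.
6. **Is there an existing vehicle?** Yes. Section 6.2 has patients complete a 2-day food diary, which the research team cross-checks, with a call for clarification if needed. Table 1 schedules nutritional intake at T1 and T2.

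**The case against.** The strongest reply is that adverse events are scheduled. Table 1 lists them at T1, T2 and T3 for everyone, so a reader who infers that they are not collected at all goes too far. That stands. What is missing is the method, not the visit.

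A second reply is that another form may capture symptoms. The PG-SGA is completed by the patient and a research team member at T1 and T2. The documents do not reproduce its items and assign it to nutritional status, not to adverse events, so they do not settle whether it would serve. If the sponsor intends that use, it should say so.

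Third, letting a pilot decide on a diary is a legitimate way to limit burden. The food is already served throughout the hospital, monitoring is classed as negligible risk, and safety is not among the objectives. These facts keep the point minor, but they do not reconcile 6.2 with 6.3.

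A reader might also infer that frequent meal deliveries give intervention patients more chances to report, and so would produce a false excess of complaints in that arm. The documents do not support this. Sections 5.1 and 6.4 give FoodforCare meal tailoring, delivery and contact about the measurements, but no role in adverse events. The instruction in 6.3 to contact staff is not limited to one arm. The filter in 7.2.1 leaves no control count, and section 8 plans no comparison.

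**Conclusion.** The point holds as a minor one. Section 6.3 depends on an instrument that 6.2 leaves undecided and Table 1 omits. If it is dropped, the plan describes no solicited collection of the named symptoms and no defined baseline for them. The conclusion is conditional on the pilot's decision, which the documents do not report, and assumes that no other form is meant to serve as the symptom record.

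The size cannot be given as a number from these documents. The effect is confined to the description of tolerability; the change in handgrip strength and the sample size are unaffected. Nor do the documents show that the no-added-risk statement in 5.3 is wrong. That section rests it on product standards and food-safety criteria, and the trial does not set out to test it.

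**What to change.** Reconcile 6.2, 6.3 and Table 1 by making symptom recording unconditional in both arms:

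- Add a short checklist (nausea, vomiting, other gastrointestinal complaints, allergic reaction) to the food diary at T1 and T2. Word the T2 questions to cover the whole three weeks, not only the two diary days.
- Name the checklist in 6.3 and Table 1 as the method for the adverse-event row at T1 and T2, and state how the row is completed at T3.
- Replace the conditional sentence in 6.2 accordingly.
- In section 8, plan a descriptive summary by arm of symptoms new or worse since T1. Include all checklist answers regardless of the causal filter in 7.2.1, since that filter would empty the control column.

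The cost is a few extra questions on an existing form, some data entry and small text edits. The limits should be acknowledged: the answers remain unblinded self-report, Table 1 places randomisation before T1 so even the baseline may be given with the allocation known, and recall over three weeks is imperfect. The gain is that both arms are asked the same questions at the same times, with a baseline.

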6.4 Study procedure

A number of things will be set in motion after the patient signs the informed consent. As described earlier, the researcher will register the patient. If the patient is allocated to the intervention group, FoodforCare will be informed by the researcher. FoodforCare will take care of the delivering of the products and will have contact with the research assistants about the measurements. Before the start of the intervention, an individual intake will take place with the patient by FoodforCare. During this intake, the composition of the dishes will be tailored to the needs of the patient in terms of composition, diet, taste, flavor and portion size. These dishes will be delivered to the patients by FoodforCare every three days. Depending on the patient's wishes, the partner or caregiver of the patient can receive the same dishes. In case the patient is allocated to the control group, the research assistants are informed to perform the measurements at home at the given time points.

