3. STUDY DESIGN

This is a randomized controlled trial (RCT). Given the nature of the intervention it is not possible to blind participants and investigators. This study will be conducted at the Radboud University Medical Center. This study will be directed according to the principles of the World Medical Association Declaration of Helsinki (64th WMA General Assembly, October 2013).

[figure not shown]

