3.1 Recruitment

Surgical patients will be screened at the preoperative out-patient clinic for risk of malnutrition with the MUST (Malnutrition Universal Screening Tool) score by nurses. In case of a score ≥ 1 , which indicates a risk for malnutrition and a potential participant, nurses will ask the participant whether they are happy to receive information about the study and will subsequently call the coordinated researcher. The researcher will conduct the initial screening and will inform the patient about the study. The patient will also be informed that participation is voluntary and withdrawal is possible at any time. The patient will receive an information leaflet with further information. A minimum of 24 hours later the researcher will contact the patient by telephone and ask whether he/she will participate in the study. After that, the informed consent form will be signed by the patient and send to the researcher, who will register the patient. The medical attending staff provided permission to approach individual patients.

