3.2 Randomization and blinding

The researcher will randomize the patient by using a password-protected randomization service which is part of the clinical data management system "Research Manager". Participants are randomized to either the intervention or the control group, using block randomization, stratified for underlying disease and MUST score (MUST1 or MUST $>$ 1). After randomization, the system provides a trial participants number, who will be documented in a designated source document with the patient information. The study number and birth date will be listed on all study documents. Blinding seems not possible for the coordinating researcher, since one group will receive FoodforCare and the other group will receive no additional products. Whether blinding is possible for the researcher will be examined during the pilot study. In that case, patients will be asked not to tell the researcher in which group they are allocated. Patients have to be aware of the group allocation. Any important protocol modifications will be communicated with the Medical Ethics Committee.

Figure 1. Study design

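### Randomisation precedes the T1 baseline and no visible text withholds allocation until T1 is recorded; a cheap change of order would protect the baseline (minor to moderate)

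*Combined protocol and SAP*

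**What the plan says.** All references are to the combined protocol and SAP.

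- **Order of events.** Table 1 (section 6.3) marks informed consent and randomisation in the column "Contact by telephone". Handgrip strength, weight, PG-SGA, nutritional intake, SF-36 and SPPB are first marked in the next column, T1 Baseline. Section 3.1 has the same sequence up to registration: "After that, the informed consent form will be signed by the patient and send to the researcher, who will register the patient".
- **Who knows the arm.** Section 3.2: "Patients have to be aware of the group allocation", and "Blinding seems not possible for the coordinating researcher". It leaves blinding of the researcher to the pilot study; if that proves feasible, patients will be asked not to disclose their arm to the researcher. Section 6.1 repeats that the pilot will decide. Section 3 says that "it is not possible to blind participants and investigators".
- **What follows allocation.** Section 6.4: "If the patient is allocated to the intervention group, FoodforCare will be informed by the researcher". FoodforCare then "will have contact with the research assistants about the measurements" and holds an individual intake before the intervention starts. For the other arm: "In case the patient is allocated to the control group, the research assistants are informed to perform the measurements at home".
- **Use of the baseline.** Section 8.2 compares percentage change in handgrip by ANCOVA and names no covariate. Section 8.3 compares changes in quality of life and functional status by t-test.

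The documents do not say when the patient or the assistants learn the arm, whether the intake comes before or after T1, or whether the research assistants and the researcher are the same people.

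**The concern.** A baseline recorded before anyone knows the arm cannot be affected by it. One recorded afterwards can be, and randomisation does not balance a difference that arises after allocation. Grip strength depends on effort. The 2-day food diary and SF-36 are self-reported, the PG-SGA is partly so, and the SPPB is a performance test. A patient who has just learned of being allocated to free meals, or to no meals, could plausibly perform or report differently. Weight on a calibrated scale is less exposed.

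Any such shift enters the estimated treatment effect: in full for an unadjusted change, and in proportion to the baseline-to-end correlation when the analysis adjusts for baseline. The different routes to the measuring staff raise a second, smaller issue. If the pilot leads to blinded assessors, contact from the meal provider about an intervention patient could identify the arm.

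**Working it through.** The plan gives no figure for this point, so the check asks how much a shift at T1 would matter.

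**Inputs from section 4.4.** SD 5 kg, baseline mean 28 kg, target difference 2 kg (7%), two-sided alpha 0.05, correlation ρ = 0.3, drop-out 20%, total 228. The 228 follows from the plan's own steps: 209 × 1.2 = 250.8, taken as 251; 251 × (1 − 0.3²) = 228.4, taken as 228. Evaluable number: 228 × 0.8 = 182. Using 228/1.2 = 190 changes little (7.2% in place of 7.1% in the first row below).

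**Assumptions, not in the documents.** Equal arms; no true effect; baseline as the ANCOVA covariate (inferred from the ρ adjustment in section 4.4); the size and direction of every shift; and ρ = 0.8 as a sensitivity value.

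**Formulas.** Let b1 and b2 be the arm-related shifts at T1 and T2.
- ANCOVA bias = b2 − ρ·b1. Residual SD = 5·√(1 − ρ²), which is 4.77 kg at ρ = 0.3 and 3.00 kg at ρ = 0.8.
- Standard error = residual SD × √(4/182), which is 0.707 kg and 0.445 kg.
- Rejection rate from the noncentral t distribution with 179 degrees of freedom and noncentrality bias/SE.

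| Shift (kg) | ρ | Size of bias (kg) | Type I error |
|---|---|---|---|
| T1 only, 1.0 | 0.3 | 0.30 | 7.1% |
| T1 only, 0.5 | 0.3 | 0.15 | 5.5% |
| T1 only, 1.0 | 0.8 | 0.80 | 43% |
| T1 only, 0.5 | 0.8 | 0.40 | 14.6% |
| Both visits, 1.0, same direction | 0.3 | 0.70 | 17% |
| Both visits, 1.0, opposite directions | 0.3 | 1.30 | 45% |
| T2 only, 1.0 (what remains after the fix) | 0.3 | 1.00 | 29% |

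**Primary percentage change without baseline adjustment** (simulation, mean 28 kg, ρ = 0.3): a T1-only shift of 1 kg gives about 3.8 percentage points and 20% type I error; 0.5 kg gives about 1.9 points and 9%.

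**Secondary change t-tests**, with an assumed correlation of 0.3: SD of change = √(2 × 0.7) = 1.18 SD, standard error = 1.18 × √(4/182) = 0.175 SD. A T1-only shift of 0.1 SD gives 9% type I error; 0.2 SD gives 21%. An equal 0.2 SD shift at both visits cancels under the present order (5%) but leaves 21% after the fix.

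**When the fix lowers bias.** The fix sets b1 to zero, so bias falls when |b2| < |b2 − ρ·b1|, that is, when b2/b1 < ρ/2. The T2 shift must be opposite in direction to the T1 shift or less than 15% of it at ρ = 0.3 (40% at ρ = 0.8). For unadjusted change the limit is 50%.

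**The case against.** The strongest objection is that the fix need not reduce bias. Patients know their arm at T2 under either order. If the same tendency acts at both visits, the present order partly cancels it: 0.70 kg now against 1.0 kg afterwards at ρ = 0.3, and at ρ = 0.8 an ANCOVA type I error of 7% now against 61% afterwards. This stands and limits what can be claimed. It does not make the present order a safeguard, because it relies on two unmeasured biases offsetting each other.

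Second, the primary effect is small at the plan's own ρ, and no document supports any particular shift. This also stands. The qualification is that the smallness depends on ρ = 0.3 and on a baseline covariate that section 8.2 does not name.

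Third, there are partial safeguards: standardised JAMAR measurement, a calibrated scale, and the request that patients not disclose their arm. That request depends on the pilot and does nothing about the patient's own knowledge.

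Fourth, much of this rests on silence. Randomising at the telephone contact does not prove that anyone knows the arm at T1, and Figure 1, which might show the sequence, could not be checked.

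A reader might infer that the baseline is biased, that FoodforCare is the only or first notice the assistants receive for intervention patients, or that this contact defeats assessor blinding. The documents support none of these. Section 6.4 does not give the timing or content of the contact, and the plan does not promise blinded assessors.

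**Conclusion.** The point holds as a minor to moderate design improvement. Randomisation is placed before T1, patients must know their arm, and no visible text withholds it until T1 is complete. Knowledge of allocation can therefore reach the baseline used in the primary percentage change and in the secondary change tests. The arm-specific contact in section 6.4 could reveal the arm if assessor blinding is adopted.

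For a T1-only shift, the effect on a baseline-adjusted primary test is small at ρ = 0.3 and substantial only if ρ is much higher; the unadjusted secondary tests are more exposed. These sizes rest on assumed shifts, 182 evaluable patients and no true effect. The gain is a baseline free of allocation effects. It would be wrong to conclude that the fix lowers total bias under every pattern.

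**What to change.** 1. In Table 1 and sections 3.2 and 6.4, randomise only after the T1 measurements are recorded, including the baseline food diary. At the least, release the allocation to the patient, FoodforCare and the assistants only then.
2. Arrange T1 and T2 in both arms by one identical route through the coordinating researcher, without FoodforCare contact with the measuring assistants.
3. State in section 3.2 who measures handgrip, and reconcile section 3 with sections 3.2 and 6.1 on assessor blinding.
4. Acknowledge as a limitation that patients still know their arm at T2, and that same-direction shifts at both visits would no longer partly cancel.

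**Cost.** Protocol wording, one extra telephone call per patient, and scheduling work for the coordinating researcher; no added patients. Home measurement is stated explicitly only for controls, so the arrangement for the intervention arm needs to be written down. The intake and first delivery would start some days later, including up to 2 days if the diary is kept after the T1 visit. Inclusion at least 4 weeks before surgery less a 3-week intervention leaves about one week, part of which consent may already use. The sponsor should confirm that this is enough.
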